## 6.2 Definition of Dose-Limiting Toxicity

Toxicity will be assessed using the NCI's CTCAE version 5.0. A DLT is defined as an AE or abnormal laboratory value assessed as being at least possibly related to the study medication, which occurs within 60 days after the second cycle of Sn-117m-DTPA.

A DLT is defined as:

### **Hematologic DLT**

- Grade  $\geq 3$  neutropenia or thrombocytopenia lasting  $\geq 14$  days
- Grade  $\geq 3$  thrombocytopenia with bleeding lasting  $\geq 14$  days

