## 2.2.4 Clinical Safety

### 2.2.4.1 Phase 1/2 Dose-ranging Study

The phase 1/2 dose-ranging study found decrease in total white blood cell count to be the only significant toxicity (Srivastava *et al.*, 1998). While the incidence of leukopenia was highest in the highest dose group (5/12 evaluable patients, 42%), severe toxicity was uncommon. Three patients (two at 10 mCi/70 kg and one at 16 mCi/70 kg) developed grade 3 neutropenia. One patient, treated with 5 mCi/70 kg, developed grade 4 neutropenia. The investigators attributed all these instances of neutropenia to chemotherapy administered following Sn-117m-DTPA administration. No patient exhibited significant thrombocytopenia. One patient reported pruritus the day after dosing; this was controlled by antihistamines. Mean decrease in total white cell count was  $1,870 \pm 1,450$  cells/mcL; mean decrease in platelet count was  $66,000 \pm 64,600$ /mcL. No dose-response trend was noted for either white cells or platelets. Nadirs were at  $34 \pm 16$  days (n=35) for total white blood cells and  $41 \pm 26$  days (n=34) for platelets.

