## 6. TREATMENT PLAN

### 6.1 Agent Administration

Treatment will be administered on an outpatient basis. Reported adverse events and potential risks are described in Section 10. Appropriate dose modifications are described in Section 7. No investigational or commercial agents or therapies other than those described in Sections 6.1 and 6.3 may be administered with the intent to treat the patient's malignancy.

Study Regimen Description				
Agent	Dose	Route	Schedule	Cycle Length
Sn-117m-DTPA	20 mCi/70 kg (0.28 mCi/kg)	Slow IV injection over 10 min	Day 1	8 weeks*

\*Treatment continues for 2 cycles.

**Retreatment** after 2 cycles is allowed after an evaluation of AEs if:

- pain ( $\geq 4$  on 11-point intensity scale) recurs within 6 months after a 16-week pain observation period  
AND
- no disease progression on bone scans ( $\leq 2$  new bone lesions), or evidence of clinical progression (such as development of cancer-related symptoms)

Patients will be administered two additional cycles (8 weeks apart) if they meet the retreatment criteria. The maximum treatment dose per patient is four injections in this study.

Patients will be instructed to maintain a high fluid intake (drink at least two to three quarts of fluid every 24 hours) for 2 weeks after each Sn-117m-DTPA treatment to minimize a concentrated radioactive excretion. In general, drinking alcoholic beverages should be kept to a minimum or avoided completely. Patients will be educated on hygiene instruction/precautions on post-therapy treatment (see Appendix I).

Required Criteria for Each Re-Treatment:

Patients must have adequate organ and marrow function as defined below to be eligible for subsequent treatments after the first treatment administration:

- leukocytes	$\geq 2,000/\text{mcL}$
- absolute neutrophil count	$\geq 1,000/\text{mcL}$
- platelets	$\geq 75,000/\text{mcL}$
- hemoglobin	$\geq 8.0 \text{ g/dL}$
- total bilirubin	$\leq 2.5 \times \text{institutional ULN}$
- AST(SGOT)/ALT(SGPT)	$\leq 5 \times \text{institutional ULN}$
- creatinine*	$\leq 1.7 \text{ mg/dL}$
	OR
- glomerular filtration rate (GFR)	$\geq 50 \text{ mL/min}/1.73 \text{ m}^2$ (see Appendix B)

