### **Non-hematologic DLT**

- Grade 3 or 4 toxicity at least possibly related to study treatment and not reversible to grade  $\leq 1$  within 24 hours, spontaneously or with standard supportive measures (e.g., antiemetics, electrolyte replacement), EXCEPT:
  - o Grade 3 nausea/vomiting or diarrhea that lasts  $< 72$  hours
  - o Grade 3 fatigue that lasts  $< 7$  days
  - o Grade  $\geq 3$  electrolyte abnormality that lasts  $< 72$  hours, unless the patient has clinical symptoms, in which case all grade 3 electrolyte abnormalities count as DLT.
  - o Grade 3 amylase or lipase elevation without associated symptoms or clinical manifestations of pancreatitis

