### 6.4 Duration of Therapy

In the absence of treatment delays due to adverse event(s), treatment may continue for 2 cycles or until one of the following criteria applies. Re-treatment is allowed upon AE evaluation if pain re-occurs within 6 months after a 16-week pain observation period.

- Disease progression
- Intercurrent illness that prevents further administration of treatment
- Unacceptable adverse event(s), defined as DLT in Section 6.2
- Patient decides to withdraw from the study
- General or specific changes in the patient's condition render the patient unacceptable for further treatment in the judgment of the investigator
- Clinical progression
- Patient non-compliance

- Termination of the study by sponsor
- The drug manufacturer can no longer provide the study agent

The reason(s) for protocol therapy discontinuation, the reason(s) for study removal, and the corresponding dates must be documented in the Case Report Form (CRF).

If a patient is withdrawn from the study during the treatment period (and will not return for any more visits), he will be encouraged to come to safety follow-up visits at 4 weeks and 12 weeks after his last Sn-117m-DTPA administration.

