## 7. DOSING DELAYS/DOSE MODIFICATIONS

No Sn-117m-DTPA dose modification is allowed. Patients will be monitored continuously for AEs throughout the study. Patients must be instructed to notify their physician immediately for any and all side effects. Treatment interval is scheduled every 8 weeks or every 56 days with a window period of +/- 7 days for all time points. If the treatment needs to be delayed due to an adverse event, study drug administration can be delayed up to 8 weeks for recovery, with the following conditions:

- Hematological toxicities must resolve to CTCAE grade 1 or less (or, if abnormal at baseline, not more than one grade above baseline) prior to administration of the next Sn-117m-DTPA dose. In the absence of recovery after 4 weeks, patients are to discontinue further study drug administrations.
- Non-hematological toxicities must resolve to CTCAE grade 2 (gastrointestinal events) or grade 3 (other toxicities) prior to administration of the next dose.
- If patients experience spinal cord compression during the treatment phase, Sn-117m-DTPA administration can continue with up to a 4-week delay if the patient is adequately treated with steroids, local SBRT, or surgery.
- If patients experience traumatic fracture in weight-bearing bones during the treatment phase, the study drug administration should be delayed 4 weeks from the fracture.

As a general approach, it is suggested that all AEs be managed with supportive care when possible at the earliest signs of toxicity.

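### The bleeding DLT in section 6.2 repeats the 14-day clause, so a shorter grade ≥3 thrombocytopenia with lesser or quickly reversed bleeding is not a DLT and has no bleeding-specific stop

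*Combined protocol and SAP*

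**What the plan says.** Section 6.2 defines a DLT as an event at least possibly related to study drug, within a window ending 60 days after the second cycle. The hematologic list has two items, both at grade ≥3:

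- neutropenia or thrombocytopenia lasting at least 14 days;
- "thrombocytopenia with bleeding lasting" at least 14 days.

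A bleed can also qualify under the non-hematologic list, which requires "Grade 3 or 4 toxicity at least possibly related to study treatment and not reversible to grade" ≤1 within 24 hours. Bleeding is not among that list's exceptions.

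The definition has two uses. Section 6.4 ends treatment for "Unacceptable adverse event(s), defined as DLT in Section 6.2". Section 9.1 suspends the study if the lower limit of the exact 95% interval for the DLT rate exceeds 30%.

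Other rules govern re-dosing. Section 7 states that "Hematological toxicities must resolve to CTCAE grade 1 or less", or to no more than one grade above an abnormal baseline, and it discontinues patients who have not recovered after 4 weeks. Section 6.1 sets a platelet floor of 75,000/mcL for later injections, and retreatment "after 2 cycles is allowed after an evaluation of AEs if" pain recurs without progression. Section 6.4 also lets the investigator stop treatment, and section 10.3.4 requires expedited reporting of grade ≥3 marrow toxicity.

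**The concern.** The apparent reason for a separate bleeding item is that bleeding makes a low platelet count more serious, so that a shorter episode should count. With the same 14-day clause on both items, bleeding never shortens the required duration of the low count.

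At stake is the individual patient rather than the trial's error rates. A patient may have a brief grade ≥3 thrombocytopenia with a clinically relevant bleed, recover, and then meet every count-based criterion for the next injection. No rule makes the bleed itself a reason to stop.

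Two features of the plan make a short episode plausible. Section 6.3.1 permits platelet transfusion, and section 6.2 does not say how transfused counts are handled. The 24-hour reversal rule also accepts reversal with standard supportive measures. Platelet count decrease is a listed possible effect of the agent (section 10.1.1.1). Section 2.2.6 warns of more marrow suppression after cytotoxic chemotherapy, which section 3.1.2 allows.

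**Working it through.** **Step 1: the logic of the definition.** The documents give no figure to reproduce here, so the check lists the cases. Every row is an at least possibly related grade ≥3 thrombocytopenia.

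| Low count lasts | Bleeding | Item 1 | Item 2, 14 days = low count | Item 2, 14 days = bleeding | Non-hematologic |
|---|---|---|---|---|---|
| ≥14 days | any or none | DLT | adds nothing | adds nothing | not needed |
| <14 days | grade 1–2, under 14 days | no | no | no | no |
| <14 days | grade 1–2, 14 days or more | no | no | DLT | no |
| <14 days | grade 3–4, reversed to ≤1 within 24 h | no | no | no, unless residual bleeding lasts 14 days | no |
| <14 days | grade 3–4, not reversed within 24 h | no | no | only if it lasts 14 days | DLT |

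If the clause describes the low count, item 2 is a subset of item 1. If it describes the bleeding, item 2 adds only bleeds of two weeks or more. Rows 2 and 4 are the gap under both readings; row 3 joins it under the first.

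**Step 2: which gap patients reach another injection.** Section 7 removes those not recovered after 4 weeks, and section 6.1 removes those below 75,000/mcL. Those who recover in time remain. None of the section 6.1 or section 7 criteria refers to a previous bleed.

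**Step 3: timing.** Section 2.2.4.1 reports the platelet nadir at 41 ± 26 "days (n=34) for platelets". Section 7 says: "Treatment interval is scheduled every 8 weeks or every 56 days with a window period of" ±7 days. Assuming roughly normal nadir times:

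- before day 49: Φ((49 − 41)/26) = Φ(0.308) = 62%
- before day 56: Φ((56 − 41)/26) = Φ(0.577) = 72%
- before day 63: Φ((63 − 41)/26) = Φ(0.846) = 80%

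These are nadirs of any depth, not of grade ≥3 episodes. They show only that a nadir after injection 1 would usually come before the decision on injection 2.

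**Step 4: frequency.** The documents give no rate for thrombocytopenia with bleeding. Section 2.2.4.1 says "No patient exhibited significant thrombocytopenia". Reading that as zero grade ≥3 events (an assumption), the exact two-sided 95% upper limit is 1 − 0.025^(1/n):

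- n = 47 (all treated): 7.5%, or 25 × 0.0755 = 1.9 of 25 patients
- n = 34 (with platelet nadir data): 10.3%, or 25 × 0.1028 = 2.6 of 25 patients

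These limits cover all significant thrombocytopenia in that study, including episodes without bleeding, episodes of 14 days or more, and patients who would not recover in time. The gap is a fraction of them and may be empty.

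**Step 5: the suspension rule.** Exact lower limits are 6/10 = 26.2%, 7/10 = 34.8%, 12/25 = 27.8% and 13/25 = 31.3%. Suspension therefore needs 7 DLTs in 10 patients or 13 in 25. The documents give no usable DLT rate, so the base rates below are assumed, and the whole 10.3% limit is added as an extreme case.

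| Assumed base DLT rate | P(≥7 of 10): base → base + 10.3% | P(≥13 of 25): base → base + 10.3% |
|---|---|---|
| 5% | <0.001% → 0.02% | <0.001% → 0.002% |
| 10% | 0.001% → 0.09% | <0.001% → 0.04% |
| 20% | 0.09% → 1.1% | 0.04% → 1.9% |

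Even then the chance of suspension stays below 2%. The thresholds themselves do not move.

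**The case against.** The strongest reply is that re-dosing after a brief, recovered thrombocytopenia with minor bleeding is a defensible choice in a palliative trial, and that the plan has other protections. Much of this stands. The 4-week rule in section 7 is a mandatory stop for patients who do not recover. In cycle 1, blood counts are due at weeks 1, 2, 4, 6 and 8, so a grade ≥3 count still present at the next two-weekly test is close to meeting the first item anyway. Grade ≥3 marrow toxicity is reported promptly, and safety can be reviewed at any time.

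The consequence before injection 2 also depends on the DLT window. Section 6.2 can be read as covering cycle 1 and running to 60 days after cycle 2, which fits its use in section 6.4 as a stop during treatment. It can also be read as covering only the 60 days after cycle 2. On that narrower reading, rewording the item would not create a stop before injection 2 and would bear only on later retreatment.

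Making bleeding of any grade a DLT would go too far, because a trivial bleed could then end palliative treatment.

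The reply does not explain the second item. If brief thrombocytopenia with bleeding was meant to be acceptable, the item has no purpose on one reading and very little on the other.

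**Conclusion.** The point holds in a limited form. The second hematologic DLT does not work as a separate bleeding criterion, and the two groups identified in the working fall outside the DLT definition, the section 9.1 DLT rate and the section 6.4 DLT stop. For those whose counts recover in time, no bleeding-specific stop applies before retreatment, or before injection 2 if the window covers cycle 1.

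Three stronger readings are not supported:

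- A reader might infer that bleeding with low platelets never counts as a DLT. Bleeding during a low count of 14 days or more counts under the first item, and an unreversed related grade 3–4 bleed counts under the non-hematologic list.
- A reader might infer that such patients can be re-dosed without restraint. The recovery rule, the 4-week discontinuation, the platelet floor and investigator judgment all apply.
- A reader might infer that study-level safety monitoring is compromised. On the assumed rates shown, the effect on the 30% rule is negligible.

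The number of patients affected cannot be estimated from the documents. It should be small and may be zero. The case for a change is that the item does not do its apparent job, that the consequence for one patient could be serious, and that correction is cheap.

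**What to change.** In section 6.2, replace the second hematologic item with: *Grade ≥3 thrombocytopenia with grade ≥2 bleeding*, with no duration. *With clinically significant bleeding* would also serve if the sponsor prefers a clinical judgment. Leave the first item and the non-hematologic list unchanged. To make the stop effective before injection 2, state in the same section that the DLT window starts at the first injection.

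No new assessment is needed, because bleeding is already collected as an adverse event and platelets are on the section 11 schedule. Sample size, power and suspension thresholds do not change. The downside is a slightly higher reported DLT rate and an occasional patient losing a later palliative injection. The grade ≥2 floor limits that loss and deliberately leaves grade 1 bleeding outside the definition.

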### **Non-hematologic DLT**

- Grade 3 or 4 toxicity at least possibly related to study treatment and not reversible to grade  $\leq 1$  within 24 hours, spontaneously or with standard supportive measures (e.g., antiemetics, electrolyte replacement), EXCEPT:
  - o Grade 3 nausea/vomiting or diarrhea that lasts  $< 72$  hours
  - o Grade 3 fatigue that lasts  $< 7$  days
  - o Grade  $\geq 3$  electrolyte abnormality that lasts  $< 72$  hours, unless the patient has clinical symptoms, in which case all grade 3 electrolyte abnormalities count as DLT.
  - o Grade 3 amylase or lipase elevation without associated symptoms or clinical manifestations of pancreatitis

## 6.3 General Concomitant Medication and Supportive Care Guidelines

### 6.3.1 Concomitant Prostate Cancer Therapy

- Patients receiving bisphosphonates or denosumab prior to enrollment can maintain therapy throughout all or part of the study. The bisphosphonate may be stopped or

started at the discretion of the investigator throughout the study (*i.e.*, both treatment phase and follow-up). Injection of bisphosphonates should be done at least 2 hours before or after study drug administration.

- Patients who have not undergone bilateral orchiectomy are allowed and should receive LHRH agonists or antiandrogen such as bicalutamide throughout the study (*i.e.*, both treatment phase and follow-up).
- Cytotoxic chemotherapy, androgen receptor blockers, androgen biosynthesis inhibitors, other systemic radioisotopes, hemi-body external radiotherapy, and other investigational drugs should not be used during the treatment period. These treatments can be given if at least 8 weeks after the last injection.
- Colony stimulating factors (*e.g.*, erythropoietin and granulocyte colony stimulating factors) and transfusions products (*e.g.*, red blood cell transfusion, and/or platelet transfusion) as dictated by standard practice are acceptable while the subject is enrolled in the study.

#### 6.3.2 Analgesic Use

Use of all analgesic medications is allowed throughout the study, including all opioid types.

#### 6.3.3 Drug-Drug Interactions

Because there is a potential for interaction of Sn-117m-DTPA with other concomitantly administered drugs, the case report form must capture the concurrent use of all other drugs, over-the-counter medications, or alternative therapies.

### 6.4 Duration of Therapy

In the absence of treatment delays due to adverse event(s), treatment may continue for 2 cycles or until one of the following criteria applies. Re-treatment is allowed upon AE evaluation if pain re-occurs within 6 months after a 16-week pain observation period.

- Disease progression
- Intercurrent illness that prevents further administration of treatment
- Unacceptable adverse event(s), defined as DLT in Section 6.2
- Patient decides to withdraw from the study
- General or specific changes in the patient's condition render the patient unacceptable for further treatment in the judgment of the investigator
- Clinical progression
- Patient non-compliance

- Termination of the study by sponsor
- The drug manufacturer can no longer provide the study agent

The reason(s) for protocol therapy discontinuation, the reason(s) for study removal, and the corresponding dates must be documented in the Case Report Form (CRF).

If a patient is withdrawn from the study during the treatment period (and will not return for any more visits), he will be encouraged to come to safety follow-up visits at 4 weeks and 12 weeks after his last Sn-117m-DTPA administration.

## 6.5 Duration of Follow-Up

Patients will be followed every 2 weeks during treatment (16 weeks), then every 4 weeks until Week 28, and then every 3 months or as clinically indicated for 12 months after the first Sn-117m-DTPA dose or until death, whichever occurs first. After the 1-year follow-up period, dates of death will be collected for all patients until the final patient completes his 1-year follow-up. Patients removed from study for unacceptable adverse event(s) will be followed until resolution or stabilization of the adverse event.

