A: Sn-117m-DTPA: 20 mCi/70 kg (0.28 mCi/kg) slow IV injection over 10 min on C1D1 and C2D1

\*Patients can be retreated if pain recurs within 6 months after 16-week pain observation period

a: Follow-up visit evaluation. Every 3 months or as clinically indicated up to one year from the first dose injection or disease progression

b: Albumin, ALP, total bilirubin, bicarbonate, BUN, calcium, chloride, creatinine, glucose, LDH, sodium, potassium, total protein, SGOT [AST], SGPT [ALT].

c: Pre-treatment daily baseline pain and analgesic use for 7 days (at least 4 out of 7 days) is required before treatment initiation. Patients will be asked to report their pain at its worst in the last 24 hours and analgesic use (stable/reduced/increased) by digital version every 2 weeks through Week 28, followed by routine clinic follow up or when they experience new pain during off-visit. **A full short version of brief pain inventory (BPI) will be asked at baseline, after Cycle 1, after Cycle 2, and at Week 24.**

d: PRO-CTCAE survey items will be assessed by digital instruments. Beginning at Week 28, surveys are requested every 3 months for 6 months after the last study treatment administration.

e: Serial DTPA dosimetry scans (optional) will be obtained at 1 hour, 4 hours (or within 4-6 hours), 24 hours (or within 16-24 hours), 48 hours (or within 36-48 hours), 72 hours (or within 60-72 hours), 1 week (+/2 days), and 4 weeks (+/2 days) post-infusion. The dosimetry scan will only be performed with first cycle of injection.

f: Urine collection for urinalysis will be collected at the indicated time points or as clinically indicated to monitor for microscopic or macroscopic hematuria as part of genitourinary toxicity monitoring.

g: Imaging: Follow up tumor response will be evaluated by CT scan of abdomen and pelvis, bone scan and chest X-ray. If Chest X-ray shows abnormal or clinically symptomatic, then CT chest should be obtained. Follow-up scans at every 8 weeks will be performed as clinically indicated, per institutional standards. PSMA PET CT scan at baseline is also acceptable.

*NCI Protocol #: 10437*

*Version Date: January 10, 2022*

h: Blood collections for research during Cycles 1 and 2 should be collected on the last day of each cycle.

i: CBC and serum chemistry should be performed 1 week before the start of Cycle 2.

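### Retreatment injections 3 and 4 require marrow checks before dosing, but no blood count is scheduled at a fixed time after them, and follow-up closes 12 months after the first dose

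*Combined protocol and SAP*

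**What the plan says.** **Retreatment.** Section 6.1: "Patients will be administered two additional cycles (8 weeks apart) if they meet the retreatment criteria". The maximum is four injections. The same section sets leukocyte, neutrophil, platelet and hemoglobin minimums for every injection after the first. Section 7 also requires hematologic toxicity to recover before the next dose.

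**Visits.** Section 6.5 sets the early schedule: "Patients will be followed every 2 weeks during treatment (16 weeks), then every 4 weeks until Week 28". Later visits run on a clock that starts at the first injection: "then every 3 months or as clinically indicated for 12 months after the first Sn-117m-DTPA dose or until death".

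**Calendar (Section 11).**
- Retreatment is marked only in the Follow-up column. The dosing legend reads "slow IV injection over 10 min on C1D1 and C2D1".
- Note a describes the Follow-up column: "Every 3 months or as clinically indicated up to one year from the first dose injection or disease progression".
- Note i times one pre-dose draw: "CBC and serum chemistry should be performed 1 week before the start of Cycle 2". The section's opening text adds a conditional repeat of laboratory tests within 48 hours before a next cycle if the patient is deteriorating.
- Counts are marked at Weeks 2, 4, 6 and 8 of Cycles 1 and 2, at Weeks 20, 24 and 28, in the Follow-up column, and at the off-study visit, which has no stated timing relative to the last dose.
- Note d is anchored to the last dose, but for patient-reported symptoms only: "surveys are requested every 3 months for 6 months after the last study treatment administration".

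**Nadirs.** Section 2.2.4.1 reports white-cell nadirs at 34 ± 16 days and platelet nadirs at 41 ± 26 days after a dose in an earlier study.

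**The concern.** After each of injections 1 and 2 the plan schedules four counts in 8 weeks. After injection 4, on the text as written, it schedules 3-monthly or as-indicated visits that end on a date fixed by the first dose. A check before injection 4 cannot show marrow suppression caused by injection 4, and no later dose exists to prompt another check.

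Low neutrophils or platelets without symptoms are seen only if blood is drawn. Section 10.3.4 requires expedited reporting of marrow toxicity of Grade 3 or higher, and objective 1.2.1 is safety by CTCAE. Both depend on a count. The documents describe repeat dosing in only three patients, who each received a second dose (Section 2.2.5), so injections 3 and 4 have no described precedent. Section 2.2.6 warns that patients with earlier chemotherapy may have more marrow suppression, and Section 3.1.2 sets no limit on prior therapies.

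**Working it through.** **1. When injection 4 can fall.** Section 9.1 gives 28 weeks as the longest follow-up needed to declare a responder. This reproduces: 12 + 16 = 28. Retreatment is allowed if pain recurs within 6 months (26 weeks) after the 16-week observation period. The start of that period is an assumption, so a range is shown. Injection 4 = injection 3 + 8 weeks.

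| Observation ends | Injection 3 (weeks) | Injection 4 (weeks) |
|---|---|---|
| Week 16 (starts at first dose) | 16-42 | 24-50 |
| Week 18 (response at Week 2) | 18-44 | 26-52 |
| Week 28 (response at Week 12) | 28-54 | 36-62 |

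To keep injection 4 within the 12-month column, the third row is cut to injection 3 in Weeks 28-42 or 28-44.

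**2. Mean nadir after follow-up closes (day 365).** The mean nadir after injection 4 falls after closure if injection 3 is later than
- white cells: (365 − 56 − 34)/7 = Week 39.3
- platelets: (365 − 56 − 41)/7 = Week 38.3

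Each start day is weighted equally:

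| Injection 3 window | White cells | Platelets |
|---|---|---|
| 16-42 (183 days) | 19/183 = 10.4% | 26/183 = 14.2% |
| 18-44 | 18.0% | 21.9% |
| 28-42 | 19.2% | 26.3% |
| 28-44 (113 days) | 33/113 = 29.2% | 40/113 = 35.4% |

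**3. No count in the 56 days after injection 4.** Assumed counts are at Weeks 20, 24 and 28, one at Week 39, 40 or 41, and one at Week 52 (day 364, a 12-month or off-study visit), all on nominal dates.
- Lowest: window 28-44, counts at Weeks 41 (day 287) and 52. Injection 4 falls on days 252-364 (113 days). Uncovered are days 287-307 (21) and day 364 (1): 22/113 = 19.5%.
- Highest: window 28-42, counts at Weeks 39 (day 273) and 52. Injection 4 falls on days 252-350 (99 days). Uncovered are days 273-307 (35): 35/99 = 35.4%, or 36/99 = 36.4% if a count on day 56 itself is not credited.

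The range is thus about 20-36%. Every timing has at most one count in those 56 days, against four after each of injections 1 and 2. Section 7 allows dates "with a window period of +/- 7 days for all time points", and Section 11 gives the same tolerance for visits. If that tolerance always helps, the low end falls to 6.2%, and two counts become possible for 3.8% of timings (window 16-42).

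**4. After injection 3.** The check before injection 4 falls at day 49 (by analogy with note i) or day 56. That is 15-22 days after the mean white-cell nadir (49 − 34; 56 − 34) and 8-15 days after the mean platelet nadir (49 − 41; 56 − 41).

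**5. What a repeated cycle schedule would cover.** Counts at days 14, 28, 42 and 56 bracket both mean nadirs. A last visit 12 weeks (84 days) after the final injection lies beyond the platelet mean plus one SD (41 + 26 = 67 days).

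**The case against.** **The ordinary reading.** Section 6.1 defines a cycle as 8 weeks and grants two additional cycles. Section 11 sets out what happens in a cycle, and Section 2.2.6 promises regular counts, citing Sections 7 and 11. On this reading the cycle columns repeat and most of the gap closes. That is reasonable, and if it is the intent, one sentence settles it. But it is not written: Section 6.5 ties 2-weekly visits to 16 weeks of treatment, and the dosing legend names Cycles 1 and 2 only. It also leaves the first-dose anchor in place, so the shares in step 2 remain if the 12-month stop applies.

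**Low consequence.** Section 2.2.4.1 reports no dose-response trend and no significant thrombocytopenia, and its investigators attributed the Grade 3-4 neutropenia to later chemotherapy. Adverse events are monitored continuously, visits as clinically indicated are allowed, and late related serious events stay reportable. Section 6.4 encourages visits at 4 and 12 weeks after the last dose, but only for patients withdrawn during treatment. These points lower the expected harm. None requires a count at a fixed time after injection 4.

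**Few patients.** Retreatment needs recurrent pain without bone-scan or clinical progression, while Section 9.4.8 counts increasing pain from a metastasis as progression. This stands.

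**Stronger readings that the documents do not support.** A reader might infer that no count at all is tied to injection 4. Sections 6.1 and 7 cannot be met without one beforehand, Section 11 has the conditional 48-hour repeat, and an off-study count exists. A reader might also infer that most timings go without a count. Figures as high as 81.4% arise only if no count is taken around Week 52, and 88.5% also needs dosing beyond 12 months, although retreatment is marked only in a column that ends at one year.

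**Conclusion.** The point holds as a gap in monitoring after dosing. Injections 3 and 4 have pre-dose criteria but no count at a fixed time afterwards, and the end of follow-up is set by the first dose whatever the date of the last. With a count near Week 52, about 20-36% of assumed timings have none in the 56 days after injection 4. With injection 4 by Week 52, about 10-35% put the mean nadir after closure.

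These shares rest on equally weighted start days, nominal visit dates unless stated, an assumed start of the observation period, no as-indicated counts, and nadir timing from an earlier study with wide SDs. They describe timings, not patients. It would be wrong to infer that follow-up must end before injection 4, or that stopping decisions are weakened: the dose-limiting toxicity window (Section 6.2) ends 60 days after the second cycle, and neither that rule nor the primary endpoint is affected. Severity is minor to moderate.

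**What to change.** - **Section 11:** state that retreatment cycles repeat the Cycle 1-2 blood count, chemistry and adverse-event rows (Weeks 2, 4, 6 and 8 after each injection). If that is already the intent, this is a clarification.
- **Section 6.5 and note a:** end safety follow-up at the later of 12 months after the first dose and 12 weeks after the last injection, an interval that Section 6.4 already uses.

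**Cost.** An amendment, plus about 7 extra routine counts with visits per retreated patient (4 + 4, less the check already needed before injection 4). As an illustration and not a bound, if 10-30% of 25 patients respond (2.5 to 7.5, so about 3 to 8) and all are retreated, that is 21 to 56 counts. The last safety visit moves later only for late-retreated patients: by 10 weeks if injection 4 is at Week 50 (50 + 12 − 52), by 12 weeks if at Week 52, and by 22 weeks if at Week 62, which requires dosing beyond 12 months. No dosing rule changes.
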